### 3.2.7 Subgroup Analyses of Efficacy

Exploratory subgroup analyses of the primary and secondary endpoints will be performed. Descriptive statistics will be provided by treatment group. Odd Ratios for wart clearance and hazard ratio for time to wart clearance will also be presented. The following subgroups will be assessed:

- Age (<18,  $\geq$ 18)
- Sex (Male, Female)
- Race (White, Non-White)
- Maximum PWA at Baseline (2,3)
- Fitzpatrick Skin Type (I, II, III, IV, V, VI)
- Number of treated warts (1 wart, 2 warts, 3 warts,  $>3$  warts)
- Subjects  $<18$  years old with 4 or more treated warts

Additionally, an analysis of wart clearance according to wart location will be performed using the individual warts as the experimental unit (i.e. the denominator). Five location categories are defined as follows based upon the grid locations as recorded on the CRF:

Subgroup	Grid Locations
Hands	'A4', 'D4', 'E4', 'H4'
Feet	'B6', 'C6', 'F6', 'G6'
Elbows	'A3', 'D3', 'E3', 'H3'
Knees	'B5', 'C5', 'F5', 'G5'
Rest of Body	All locations not included in above 4 categories

### 3.3 Safety Analyses

Safety summaries will be conducted on the Safety Population and use actual treatment received.

The following sections detail the summaries performed on the safety data. Additional data handling rules including those for imputation of partially missing dates are provided in a separate SAP document pertaining to data handling and programming specifications.

The baseline scores for vital signs, laboratory assessments and local skin reactions will be the last non-missing value collected  $\leq$  the date of the first application of double-blind study medication.

#### 3.3.1 Extent of Exposure

The duration of treatment, the number of application days (i.e. the actual count of days where an application occurred), the mean applications per wart (for each subject the sum of all applications across all treated warts and all application days divided by the total number of treatments for all treated warts), and the total applications will be summarized using descriptive statistics (n, mean, SD, median, minimum and maximum). The percentage of total wart treatments that were performed in 1, 2 or 3 applications is also provided.

Overall compliance is calculated as the number total number of warts treated for the treatment period (through date of last application to any wart) divided by the total number of warts expected to be treated. The total number of warts treated is the sum of the retreatment and home application diary records completed times the number of warts assessed at baseline minus the number of warts scored as PWA=0 or having an LSR grade 3 at the most recent assessment ( $\leq$  the date of the application).

#### 3.3.2 Adverse Events

Adverse events are coded using the MedDRA (Version 22) dictionary and are categorized by system organ class (SOC) and preferred term (PT). Only treatment emergent adverse events are included in summary tabulations (i.e. adverse events occurring on or after the first application of study medication and within 30 days following the last application of study medication). All adverse events are included in the data listings including those that are not considered treatment emergent.

To allow differentiation as to which study period an Adverse Event occurred, three categories are defined based upon onset date. Adverse Events that had onset dates prior to the first application of study medication are considered "prior". Adverse events with onset dates on or after the first application of double-blind study medication and within 30 days following the last application of study medication are considered "treatment emergent". Events with onset dates more than 30 days after the last application of study medication are considered as "post-therapy".

Frequency tabulations are presented by MedDRA SOC and preferred term, for all adverse events; study treatment-related, adverse events resulting in discontinuation of study treatment, serious adverse events and adverse events by maximum severity. Adverse events resulting in discontinuation are those with 'action taken' recorded as 'drug withdrawn'.

Treatment emergent adverse event summaries by MedDRA SOC and preferred term will also be provided according to the following subgroups:

- Age (<18, 18 to 65, and >65)
- Sex (Male, Female)
- Race (White, Non-White)

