All concomitant therapies including (topical and oral) prescription medications, over the counter medications and natural supplements and non-drug therapies including chiropractic, physical therapy, and energy-based therapy must be documented in the subject CRF. Subjects must not apply any topical products (e.g., moisturizers, sunscreen, etc.) to the identified common wart within 12 hours prior to any study visit.

The reporting period for Serious Adverse Events (SAEs) begins when the subject signs the informed consent and continues through Visit 11. Refer to Section Section 14.1.2 for instructions on the reporting of SAEs. Non-serious clinical adverse events will be collected following the application of the study medication at Visit 2 and through Visit 11. Non-serious adverse events that occur between the time of consent and study medication application will be documented as medical history. All safety reporting (AEs and SAEs) will conclude at Visit 11 (approximately 28 days after last study medication application) except for clinical adverse events related to local skin reactions.

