#### **14.1.3. Adverse Event Reporting Period**

The investigator must start reporting non-serious AEs starting with the subject’s first study medication treatment continuing until Visit 11. Non-serious adverse events that occur between the time the subject was consented and the first application of study medication will be reported as medical history.

Reporting for SAEs begins after the subject signs the informed consent and continues until Visit 11 (regardless of relationship to study medication). If a subject experiences a SAE after Visit 11 that is deemed by the investigator to be related to study medication, the investigator must report this to the Sponsor using the study specific SAE report form.

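### AE and SAE tables close 30 days after each subject's own last application, so later AE records that the protocol still collects appear only in listings

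*SAP*

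**What the plan says.** **Counting (SAP 3.3.2).** "Only treatment emergent adverse events are included in summary tabulations". An event qualifies if its onset is on or after the first application and "within 30 days following the last application of study medication". "Events with onset dates more than 30 days after the last application of study medication are considered as" post-therapy. No post-therapy table is planned, but "All adverse events are included in the data listings including those that are not considered treatment emergent". The tables for all AEs, related AEs, AEs leading to discontinuation, SAEs and maximum severity all inherit this limit.

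**Collection (Protocol).** Section 14.1.3 runs non-serious AE reporting from the "first study medication treatment continuing until Visit 11", and SAE reporting from consent to the same visit. Table 2, footnote 17 (repeated under the SAP's Schedule of Assessments) places Visit 11 "approximately 28 days after last study medication application" and ends safety reporting there "except for clinical adverse events related to local skin reactions". Section 14.1.3 adds a second continuation: "If a subject experiences a SAE after Visit 11 that is deemed by the investigator to be related to study medication", it must still go to the sponsor.

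**Dosing (Protocol 10.5).** A wart graded clear at Visits 3 to 9 is not treated at that visit or at home that week, so a subject with all warts clear stops dosing unless one recurs.

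**Local skin reactions (SAP 3.3.3).** Subjects whose signs worsen by a grade or more at any time after dosing starts are counted by arm. A separate table restricts this to 30 days after the last application.

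**The concern.** Collection ends at a fixed visit, while counting ends at a point set by each subject's own dosing. Where the second comes first, events are collected and then left out of every AE and SAE rate by arm. This happens to subjects who stop dosing early, because their warts cleared or for other reasons, and who stay in follow-up. It also happens to any late local-skin AE or related SAE reported after the cut-off. Safety of A-101 45% is a stated secondary objective, and a listing does not give a rate by arm. Because clearance shortens dosing, the length of the counting window also depends in part on response.

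**Working it through.** **Inputs.** Visit days (Visit 11 = Day 78, Visit 13 = Day 137) and home application days (4, 11, 18, 25, 32, 39, 46, 53) come from Protocol sections 7 and 10.5 and Table 2. The 30-day rule comes from SAP 3.3.2.

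**1. The plan's own interval.** From the last in-office application, 78 − 50 = 28 days, which reproduces footnote 17. From the last scheduled application, at home on Day 53, it is 78 − 53 = 25 days. With the visit and home windows the range is 71 − 54 = 17 to 85 − 53 = 32 days.

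**2. Routine AE days left out of the tables.** For a subject first all clear at a given visit, with no recurrence, the last application is the preceding home dose. Cut-off = last application + 30. Days left out = max(0, 78 − cut-off).

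| First all clear | Last application | Cut-off | Days left out of 78 |
|---|---|---|---|
| Visit 3 (Day 8) | 4 | 34 | 44 |
| Visit 4 (Day 15) | 11 | 41 | 37 |
| Visit 5 (Day 22) | 18 | 48 | 30 |
| Visit 6 (Day 29) | 25 | 55 | 23 |
| Visit 7 (Day 36) | 32 | 62 | 16 |
| Visit 8 (Day 43) | 39 | 69 | 9 |
| Visit 9 (Day 50) | 46 | 76 | 2 |
| Visit 10 or never (full course) | 53 | 83 | 0 |

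The zero for a full course is nominal. If Visit 11 falls on Day 85, the end of its window, 85 − 83 = 2 days are left out.

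**3. What this does to one subject's chance of being counted.** Assume a constant AE hazard with 10% risk over 78 days. The chance of being counted in a window of w days is 1 − 0.9^(w/78): 7.2% for w = 55 and 4.5% for w = 34.

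**4. After Visit 11, full course.** The tables close on Day 83, so 137 − 83 = 54 of the 137 − 78 = 59 days to Visit 13 are outside them. This matters only for local-skin AEs and related SAEs, because other AEs are not collected then.

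**5. Average difference between arms.** The documents give no timing of clearance, so this rests on assumptions. Take 16% of A-101 and 5% of Vehicle subjects fully clear; the 11-point gap matches the planned responder advantage in SAP 3.5.

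- Clearance spread evenly over Visits 3 to 10: mean days left out per clearer = (44 + 37 + 30 + 23 + 16 + 9 + 2 + 0)/8 = 20.1. Per subject this is 0.16 × 20.1 = 3.2 against 0.05 × 20.1 = 1.0, a difference of 2.2 days (2.8% of 78).
- Clearance spread evenly over Visits 6 to 10: mean = (23 + 16 + 9 + 2 + 0)/5 = 10. Per subject this is 1.6 against 0.5, a difference of 1.1 days (1.4% of 78).
- Extreme bound: apply the per-wart rates (26% v 9%) to subjects and let all clear at Visit 3. The difference is 0.17 × 44 = 7.5 days (9.6% of 78).

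**The case against.** The strongest reply is SAP 3.3.3. A reader might infer from 3.3.2 that late local effects are missing from every comparison by arm. The documents do not support that. Seven signs (erythema, edema, erosion, ulceration, vesicles/bullae, excoriations, scabbing) are assessed through Visit 13, and their worsening is tabulated by arm with no time limit. This stands and narrows the point considerably. That table does not carry relatedness, seriousness or AE severity. It also leaves out the two subject-reported symptoms (stinging/burning and pruritus), although Protocol 15.4 speaks of tabulating LSR scores generally. Nor can it show local events outside the seven signs, such as scarring or infection, which the Protocol's Introduction names as complications of existing wart procedures.

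Second, a 30-day treatment-emergent window is conventional, Protocol 15.4 itself tabulates treatment-emergent AEs, and the later events are classified and listed. This also stands, and it is why the 30-day table should stay. The 30-day limit itself comes from the SAP, however, and 3.3.3 already shows local signs both with and without it.

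Third, late collection is less settled than footnote 17 suggests. Protocol 14.1.3 stops non-serious AEs at Visit 11 with no local-skin exception, and the Adverse Events row of the schedule has no mark at Visits 12 and 13. For related SAEs, footnote 17 states no exception, while 14.1.3 requires a report on the SAE form. Section 14.2.2 asks for the AE CRF only for SAEs within the reporting period. It is therefore not established that all these records reach the clinical database.

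Fourth, a wart that recurs and is re-treated by Visit 9 resets the clock, and the 30-day tail is the same length for everyone.

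**Conclusion.** The point holds as a gap in descriptive reporting. Under SAP 3.3.2 as written, two groups of records reach listings but no AE or SAE table: routine AEs up to Visit 11 in subjects who stop dosing early, and any local-skin AEs or related SAEs after the cut-off. For an individual the nominal loss runs from 0 days (full course) to 44 of 78 (all clear at Visit 3), assuming no recurrence.

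A reader might go further and infer that the AE tables materially favour A-101. The direction is right, since more early clearance shortens the counted window, but the size does not support that reading. The average difference is about 1 to 2 days under the assumed 16% and 5%, and even the implausible extreme bound is under 10% of the routine collection period. No inferential safety test is planned, so no test result is affected. Nor should the 54 of 59 days be read as a loss of AEs in general, because only two kinds of record are in question there.

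**What to change.** In SAP 3.3.2, keep the 30-day treatment-emergent tables and add:

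1. a by-arm table of all AEs and SAEs with onset from first application through Visit 11, a window that does not depend on response;
2. a by-arm table of local-skin AEs and related SAEs with onset after Visit 11, as reported, stating whether the source is the AE CRF or the SAE form.

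Separately, reconcile footnote 17 (Protocol Table 2 and its copy in the SAP) with Protocol 14.1.3 and the schedule's Adverse Events row, on whether local-skin AEs are collected at Visits 12 and 13 and on related SAEs after Visit 11.

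The cost is SAP wording and two descriptive tables, with no new assessments and no effect on type I error. SAP 3.6 records that Version 1.2 already contains a correction made after unblinding, so tables added after that point should be labelled post hoc.

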### **3.3.3 Local Skin Reactions**

The number of subjects with local skin reaction signs that worsened by at least 1 grade from baseline any time after the first application of study medication will be tabulated according to treatment group for each sign as well any sign. A separate summary limited to LSRs that worsen and which occur within 30 days of the last application of study medication will be provided. The number of subjects with local skin reaction signs that worsened by at least 1 grade from baseline any time after the first application of study medication will be tabulated by treatment group and Fitzpatrick Skin Type for each sign as well as any sign.

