A-101 ( $H_2O_2$ ) 45% (w/w) Topical Solution administered once weekly and twice weekly was well tolerated. Treatment emergent adverse events were predominantly mild and unrelated to study medication. Local Skin Reactions (LSRs) were predominantly mild and transient. The LSRs of pruritus and stinging reported by subjects, and crusting, edema, erythema, and scaling reported by the investigator following treatment generally resolved by Visit 13 (Day 134). There were no clinically significant changes during the study in laboratory evaluations or vital signs.

Aclaris Therapeutics, Inc.

Protocol Number: A-101-WART-302

Amendment 3: Version 5 14 February 2019

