### **13.1. Local Skin Reactions (LSRs)**

The LSR assessment is the Investigator's assessment of the signs and the subject's assessment of the symptoms associated with irritation at the identified common wart site (*i.e.*, the common wart and the skin immediately surrounding the common wart exposed to study medication). The Investigator may refer to previous photographs to assist with these assessments only AFTER the PWA has been performed.

The Local Skin Reaction signs to be assessed are:

- Erythema
- Edema
- Erosion
- Ulceration
- Vesicles/bullae
- Excoriations
- Scabbing

The Local Skin Reaction symptoms to be assessed (by the Subject) are:

- Stinging/burning
- Pruritus (itch)

At Visits 2-13, the Investigator will evaluate the LSR signs at the each identified common wart site as follows:

- At visits where a study medication treatment or retreatment is performed:
  - Perform an LSR assessment prior to any study medication applicationand

At Visits 2-13, the Subject will assess the LSR symptoms at the identified common wart site as follows:

- At visits where a study medication treatment or retreatment is performed:
  - Perform an LSR assessment prior to any study medication application

At visits where **NO** study medication treatment is performed:

Aclaris Therapeutics, Inc.

Protocol Number: A-101-WART-302

Amendment 3: Version 5 14 February 2019

- Perform an LSR assessment.

The Investigator and Subject should report the one integer that best describes the severity of each LSR sign or LSR symptom for the common wart site using the scale below:

| Local Skin Reactions |  |
|-----------------------------|--|
| Grade                | Descriptor  |
| 0                           | None; No signs or symptoms present.  |
| 1                           | Asymptomatic or mild symptoms; clinical or diagnostic observations only; intervention not indicated.                               |
| 2                           | Moderate; minimal, local or noninvasive intervention indicated.  |
| 3                           | Severe or medically significant but not immediately life threatening; disabling; limiting self-care of activities of daily living. |

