#### **15.4. Statistical Analysis of Safety Data**

Descriptive statistics will be calculated on the safety parameters using the Safety Population and using actual treatment received. The proportion of subjects with treatment-emergent adverse events will be tabulated and presented by treatment and Medical Dictionary for Regulatory Activities (MedDRA) System Organ Class. Vital signs, LSR scores and clinically relevant abnormal laboratory results will also be tabulated and presented by study medication. No inferential testing will be performed.

Safety summaries by study medication group will include listings by study medication of adverse events incidences within each MedDRA System Organ Class, and changes from pre-application values in vital signs. Adverse event summaries will be presented by study medication showing the proportion of subjects experiencing adverse events, both overall and by MedDRA System Organ Class. The version of MedDRA to be used for the analysis of this study will be specified in the Statistical Analysis Plan.

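### SAP 3.3.3 specifies its whole-study and by-skin-type local skin reaction tables for signs only, so the two subject-rated symptoms have no explicitly specified summary

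*SAP*

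**What the plan says.** Protocol 13.1 describes the LSR assessment as "the Investigator's assessment of the signs and the subject's assessment of the symptoms associated with irritation". The investigator rates seven signs, from erythema to scabbing. A separate list, introduced by "The Local Skin Reaction symptoms to be assessed (by the Subject) are", holds two items: stinging/burning and pruritus. All nine items use the same 0 to 3 grade and are scored at Visits 2 to 13. The footnotes to the SAP's schedule of assessments repeat that both investigator and subject make the assessment.

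Protocol 15.4 commits to a table: "Vital signs, LSR scores and clinically relevant abnormal laboratory results will also be tabulated", presented by study medication. It does not restrict the scores to signs.

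SAP 3.3.3 has three sentences:

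- The first counts "The number of subjects with local skin reaction signs that worsened by at least 1 grade from baseline" at any time after first application. These counts "will be tabulated according to treatment group for each sign as well any sign".
- The second reads: "A separate summary limited to LSRs that worsen and which occur within 30 days of the last application of study medication will be provided".
- The third repeats the first count, which "will be tabulated by treatment group and Fitzpatrick Skin Type for each sign as well as any sign".

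The section does not mention symptoms, stinging/burning or pruritus. SAP 3.6, which lists changes and clarifications to the planned analysis, says nothing about leaving them out.

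**The concern.** In this protocol, sign is not shorthand for any local reaction. Section 13.1 gives signs and symptoms separate lists and separate raters, and the retreatment criteria in section 10.5 name both terms. A programmer working from SAP 3.3.3 would therefore build seven rows plus an any-sign row. A subject whose only worsening was stinging or itch would appear in neither the whole-study table nor the skin-type table.

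Safety is a stated secondary objective, and these two items are the only subject-rated LSR scores. They were also foreseeable: the phase 2 summary in Protocol 5.2 names "The LSRs of pruritus and stinging reported by subjects" among the reactions seen. Symptom grades also bear on exposure. A severe and worsening symptom can hold back retreatment under Protocol 10.5, and SAP 3.3.1 uses LSR grade 3 in its compliance calculation. At stake is a safety report that omits the subject's own graded account of local tolerability from its main LSR tables.

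**Working it through.** The point rests on no alpha, effect size or power figure, so the check is a comparison of texts with a few counts.

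**1. Items covered.** Protocol 13.1 lists 7 signs and 2 symptoms, so 7 + 2 = 9 items. The first and third sentences of SAP 3.3.3 cover the 7 signs. That leaves 9 − 7 = 2 items without a named row, and those 2 are all of the subject-rated items.

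**2. Data scheduled.** Visits 2 to 13 are 13 − 2 + 1 = 12 visits. Two symptoms at 12 visits give 2 × 12 = 24 scores per wart. With 1 to 6 identified warts, that is 24 to 6 × 24 = 144 scores per subject. The Visit 2 score precedes first application and serves as baseline under SAP 3.3. The post-baseline part is therefore 2 × 11 = 22 scores per wart, or 22 to 132 per subject.

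**3. The three SAP summaries against the symptoms.**

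| SAP 3.3.3 sentence | Period | Wording | Symptoms covered? |
|---|---|---|---|
| First | Any time after first application | Signs; each sign, any sign | No |
| Second | Up to 30 days from last application | LSRs | Unclear |
| Third | Any time, by Fitzpatrick type | Signs; each sign, any sign | No |

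**4. The second sentence.** It can be read in two ways. As a time-restricted version of the signs table just before it, it excludes symptoms. Under the protocol's definition of LSRs, it includes them. The wider reading still leaves a gap. The last scheduled application is Day 53, or Day 54 with the permitted window, so the 30 days end at about Day 54 + 30 = 84. Visit 12 is Day 106 with a 7-day window, hence Day 99 at the earliest, and Visit 13 is Day 137. With applications on schedule, symptom scores from these two visits would fall outside the 30-day summary, and the skin-type table would still have no symptom rows.

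**5. Declared change?** SAP 3.6 records several differences from the protocol, including the safety population, but none concerning LSR symptoms.

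**The case against.** The strongest objection is the second sentence of SAP 3.3.3. Protocol 13.1 includes symptoms in the LSR assessment, and Protocol 5.2 calls pruritus and stinging LSRs. On the documents' own usage, the 30-day summary may therefore include both symptoms. This stands. A reader might infer that symptoms get no summary at all, but the text supports only that none is explicitly specified.

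A second objection concerns versions. The SAP introduction says it was written for Protocol Amendment 2, Version 4, while the statistics section was updated in Version 5. The Version 4 wording of 15.4 is not available, so it cannot be shown that the SAP departed from the text its authors had before them. The mismatch with the current 15.4 remains, and section 13.1 is the firmer comparison. Nor does 15.4 promise every score; it is merely unrestricted.

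Third, symptoms reported as adverse events enter the AE tables. This is only partial cover. Under Protocol 14, AEs are elicited by a non-directive question and graded on a different severity scale. SAP 3.3.2 summarizes only those starting within 30 days of last application. They do not replace item-by-item 0 to 3 scores collected through Visit 13.

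Fourth, SAP 3.3 refers to a separate document, which is not available here. It is described as covering data handling and programming specifications; nothing suggests that it adds tables.

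Finally, a reader might infer that the omission makes the product look better tolerated, or that the any-sign row undercounts reactors. Neither is established. The row claims to count only signs, and the number of symptom-only subjects is unknown. Phase 2 reactions were described as mostly mild and short-lived. At treatment visits, symptoms are scored before application, so the scores may miss some acute stinging.

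**Conclusion.** The point holds as a mismatch between what is collected and what the SAP says it will tabulate. Two of SAP 3.3.3's three summaries exclude the subject-rated symptoms by their wording, the third is ambiguous, and no omission is declared. The gap is 2 of 9 LSR items, or 24 to 144 scheduled scores per subject.

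Its consequence is limited. Safety analysis is descriptive with no inferential testing, so efficacy conclusions, type I error and power do not change. The documents give no symptom rates, so neither the direction nor the size of any effect on the tolerability picture can be stated. The documents also do not require a maximum-grade display; that would be a matter of preference.

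The conclusion assumes that SAP 3.3.3 is programmed as written and that no unseen specification adds symptom rows. It is worth correcting because the plan, followed exactly, gives an incomplete safety summary.

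**What to change.** - In the first and third sentences of SAP 3.3.3, tabulate each sign, each symptom, and any sign or symptom.
- In the second sentence, state that LSRs covers both signs and symptoms.
- Record the change in SAP 3.6, with its timing relative to unblinding. SAP 3.6 shows that Version 1.2 already carries a correction made after unblinding, so an addition to this version must be documented as coming after it.

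The cost is a few extra rows in descriptive tables, built from data already scheduled for collection, plus one documented SAP change. There is no alpha cost and no added visit or assessment.

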## **14. ADVERSE EVENTS**

### **14.1. Definitions**

#### **14.1.1. Adverse Events (AEs)**

An adverse event (AE) is any untoward medical occurrence in a patient that develops or worsens in severity during the conduct of a clinical study of a pharmaceutical product and does not necessarily have a causal relationship to the study drug. An adverse event can, therefore, be any unfavorable and unintended physical sign, symptom, or laboratory parameter that develops or worsens in severity during the course of the study, or significant worsening of the disease under study (or any concurrent disease), whether or not considered related to the study drug.

Accordingly, an adverse event could include any of the following:

- intercurrent illnesses;
- physical injuries;
- events possibly related to concomitant medication;
- significant worsening (change in nature, severity, or frequency) of the disease under study or other pre-existing conditions. (NOTE: A condition, recorded as pre-existing, that is intermittently symptomatic [e.g., headache] and which occurs during the study should be recorded as an adverse event);
- Drug interactions;
- Events occurring during diagnostic procedures or any washout phase of the study;
- laboratory or diagnostic test abnormalities occurring after the start of the study (i.e., after screening and once confirmed by repeat testing) that results in the withdrawal of the patient from the study, requires medical treatment or further diagnostic work-up, or is considered by the study investigator to be clinically significant. NOTE: Abnormal laboratory test results at the screening visit that preclude a patient from entering the study or receiving study treatment are not considered adverse events, but will be recorded to monitor data from patients who do not meet screening criteria.

**Worsening of any of the identified common wart assessments should be reported as an AE ONLY if the use of the study medication is interrupted or discontinued or if therapy is required to manage the event.**

**The investigator must, for any common wart related AE, question the subject in detail to determine if there are any confounding factors (e.g., irritation by clothing or activity, sunburn) for any such AE.**

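### SAP 3.3.3 reduces the 0–3 local skin reaction grades to worsened yes/no, so no planned LSR table shows how many subjects reached grade 3 or still had a reaction during follow-up

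*SAP*

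**What the plan says.** Protocol 13.1 lists seven signs rated by the investigator (erythema, edema, erosion, ulceration, vesicles/bullae, excoriations, scabbing) and two symptoms rated by the subject (stinging/burning, pruritus). For each: "The Investigator and Subject should report the one integer that best describes the severity of each LSR sign or LSR symptom". The scale runs from 0 to 3, and grade 3 is defined as "Severe or medically significant but not immediately life threatening; disabling; limiting self-care of activities of daily living". Table 2, footnote 13, schedules these ratings for every identified wart at Visits 2–13.

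Protocol 15.4 then states: "Vital signs, LSR scores and clinically relevant abnormal laboratory results will also be tabulated and presented by study medication".

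SAP 3.3.3 plans three summaries:

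- Subjects with "local skin reaction signs that worsened by at least 1 grade from baseline any time after the first application of study medication", to be "tabulated according to treatment group for each sign as well any sign".
- A time-limited version: "A separate summary limited to LSRs that worsen and which occur within 30 days of the last application of study medication will be provided".
- The first summary again, split by Fitzpatrick skin type.

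The section plans no table by grade, worst grade, visit, duration or resolution. The rest of the SAP uses LSR grade 3 only once, in the compliance formula of 3.3.1.

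**The concern.** Safety is a stated secondary objective, and the LSR scale is the protocol's dedicated instrument for local tolerability. Grade 3 also has a role in trial conduct: under Protocol 10.5 it contributes to withholding retreatment, when the grade has also risen since the previous visit. Yet no planned summary gives its frequency.

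Protocol 5.2 summarises Phase 2 with "Local Skin Reactions (LSRs) were predominantly mild and transient" and adds that the reactions had mostly cleared by Visit 13. Severity, transience and resolution are the properties that a yes/no worsening count leaves out. On the planned LSR tables alone, Phase 3 could neither support nor correct that description, although it collects the data to do so.

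A second gap is that the two tables with the at-least-1-grade rule name signs only. The 30-day summary refers to LSRs generally, so it might include symptoms, but the text does not say so. Stinging/burning and pruritus are left without a clearly planned table.

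**Working it through.** The documents give no LSR rate and no LSR precision target, so there is no figure to reproduce. The check sets what is collected against what is tabulated, then uses labelled illustrations.

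**1. What is collected.** Nine items (7 signs + 2 symptoms), each 0–3, for each wart. Visit 2, before application, supplies baseline under the rule in SAP 3.3. Post-baseline visits are 3 to 13, that is 13 − 3 + 1 = 11. Four of these (Visits 10–13) follow the end of treatment.

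**2. What is tabulated.** One binary per subject for each sign, plus any sign. On an integer scale, any worsening is at least 1 grade, so the 30-day table is the same binary over a shorter period.

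**3. Loss of grade.** Take one sign, baseline grade 0, 250 subjects per arm (SAP 3.5), with assumed severity mixes:

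- Mix A: 200 subjects peak at grade 1, none higher. Worsened: 200/250 = 80%. Grade 3: 0/250 = 0%.
- Mix B: 100 at grade 1, 60 at grade 2, 40 at grade 3. Worsened: (100 + 60 + 40)/250 = 80%. Grade 3: 40/250 = 16%.

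The SAP row for that sign is identical in both.

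**4. Loss of persistence.** The last scheduled application is Day 53. Visits 10, 11, 12 and 13 (Days 60, 78, 106, 137) fall 60 − 53 = 7, 78 − 53 = 25, 106 − 53 = 53 and 137 − 53 = 84 days later. Compare two subjects treated to Day 53 who first worsen at Visit 9 (Day 50). One is back to baseline by Visit 10; the other still has the reaction at Visit 13. Each counts once in the any-time table and once in the 30-day table. Neither table separates them.

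**5. What a grade table would show.** Precision with 250 subjects, rates assumed:

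- If 10% reach grade 3, the 95% half-width is 1.96 × √(0.10 × 0.90 / 250) = 0.037, or 3.7 percentage points.
- The chance of seeing at least one grade 3 subject in an arm is 1 − (1 − p)^250: 71% at p = 0.5%, 92% at 1%, 99% at 2%, and close to 100% at 5%.
- Zero of 250 gives a one-sided 95% upper bound of 1 − 0.05^(1/250) = 1.2%. The upper limit of a two-sided 95% interval is 1 − 0.025^(1/250) = 1.5%.

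**6. Comparison within the SAP.** Section 3.3.4 gives vital signs by visit. Section 3.3.5 gives laboratory values by visit and shifts to the worst post-baseline category. LSRs get neither form. SAP 3.6, which lists changes to the planned analysis, does not mention LSRs.

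**The case against.** The strongest defence is the adverse event route. SAP 3.3.2 tabulates AEs by maximum severity, relatedness and discontinuation, and lists every AE, including those after the treatment-emergent period. Protocol Table 2, footnote 17, exempts LSR-related AEs from the Visit 11 reporting stop, and Protocol 14.2.1 requires related AEs to be followed to resolution or a stable outcome. A reader might therefore infer that severe reactions go unreported altogether; the documents do not support that. What remains is that a reaction enters these tables only if it was also recorded as an AE, that AE severity uses a different scale (Protocol 14.1.4), and that the AE summaries cover only onset within 30 days of the last application. None gives duration or resolution.

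Four stronger readings also fail:

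- **Mild redness and a severe ulcer are counted as the same thing.** Erythema and ulceration have separate rows and merge only in the any-sign row. The loss is between grades of the same sign.
- **Data from the post-baseline visits go unused.** The any-time rule draws on every post-baseline assessment. What is lost is grade and duration.
- **Protocol 14.1.1 keeps LSRs out of AE reporting.** It says that worsening of wart assessments "should be reported as an AE ONLY if the use of the study medication is interrupted or discontinued or if therapy is required". Whether LSRs are wart assessments is not established: they sit in the safety section and cover surrounding skin, and footnote 17 expects LSR-related AEs. Even on the narrow reading, the therapy trigger would still operate at Visits 10–13.
- **The planned table will saturate because most treated subjects redden.** The documents give no rates. At treatment visits LSRs are scored before application, about four days after the scheduled home dose (for example Day 4 to Day 8), so brief reactions may not be captured.

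It can also be said that safety reporting is purely descriptive, so grade tables could be added whenever wanted. That is true and makes the fix cheap, but the SAP as written does not commit to them. SAP 3.3 mentions a separate data-handling and programming document, which is not available here. It might specify more, although SAP 3.3 presents its own subsections as the detail of the safety summaries.

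**Conclusion.** The point holds as a reporting gap. SAP 3.3.3 dichotomises a four-level scale, does not deliver the tabulation of scores described in Protocol 15.4, and leaves the two subject-rated symptoms without a clearly planned table. The planned LSR tables cannot show whether reactions were mild, transient or resolved by Visit 13.

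Its size cannot be stated as a rate, because the documents contain no LSR frequencies. The example of 0% against 16% grade 3 behind the same 80% row shows what the table can conceal; it does not predict what will occur. The conclusion rests on the text of SAP 3.3.3 being the full LSR plan. It does not touch the primary or secondary efficacy analyses or type I error. The change should be made, but nothing in the efficacy conclusions depends on it.

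**What to change.** In SAP 3.3.3 add, by arm, for each of the seven signs and each of the two symptoms:

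- the worst post-baseline grade (0, 1, 2, 3) per subject across warts, with the number reaching grade 3 shown explicitly;
- the grade distribution by visit through Visit 13, with the number still above baseline and the number at grade 2 or higher at each of Visits 10 to 13.

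Keep the at-least-1-grade tables as supportive, and state whether the 30-day summary includes symptoms.

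A worst-grade table by age (<18, ≥18) is optional. No passage promises LSRs by age, but SAP 3.3.2 already reports AEs separately for those under 18, and about 100 subjects aged 1 to 17 are planned.

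The cost is SAP wording and a few descriptive tables from data already collected, using the LSR baseline already defined in SAP 3.3. Protocol 15.4 rules out inferential testing of safety data, so no alpha is spent. SAP 3.6 records that the correction in version 1.2 was made after unblinding, so tables added after that version should be labelled as post-unblinding additions.
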